## **5. Assessment Schedule (Table 2)**

### **1. Screening and Group Assignment Visit (-21 Days to Day 0)**

For all consenting patients, baseline demographic and clinical information was collected prior to group assignment, including: Age, gender, and smoking status (current smoker, former smoker, or non-smoker).

- (1) Use of nonsteroidal anti-inflammatory drugs (NSAIDs) or other anticoagulants.
- (2) Use of proton pump inhibitors (PPIs), H2 receptor blockers (H2RB), or other antacids.
- (3) Presence of primary sclerosing cholangitis (PSC).
- (4) History of appendectomy.
- (5) Duration and severity of ulcerative colitis (UC).
- (6) Current treatments and medications.
- (7) Self-reported medication adherence.

Eligible participants were then randomly allocated in a 1:1 ratio to two parallel groups to receive FMT from either a Han donor or a Bai donor.

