### **2. Treatment and Follow-Up (Week 0 to Week 12)**

Participants will undergo two colonoscopies with biopsies performed at two time points: before treatment, at 8 – 12 weeks post-FMT

Stool samples will be collected at the following times: before treatment, at the end of FMT treatment, 8 weeks post-FMT, 12 weeks post-FMT.

During each visit, Mayo scores (including endoscopic subscoring) were evaluated by blinded outcome assessors. Biopsies were performed for histological assessments, and histological scoring was conducted by a blind pathologist. A dedicated telephone line was available for patients to report any adverse events or worsening of symptoms between scheduled visits. All investigators were aware of group allocation, while endoscopists, pathologists, and outcome assessors remained fully blinded to group assignments to minimize assessment bias.

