### **2. Blinding Maintenance:**

This trial adopts a single-blind design, where participants will be blinded to the identity of the FMT donor, while investigators will be aware of the donor identity. The donor's identity will only be accessible to a limited number of staff responsible for preparing the FMT solutions.

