#### 11. Statistical Analysis

Continuous variables will be expressed as means (SD) and compared between groups using unpaired t-tests. Categorical variables will be compared using the chi-square test or Fisher's exact test. A modified intent-to-treat analysis will include all participants who have received at least one FMT treatment. Participants requiring additional treatment, violating the study protocol, failing to discontinue corticosteroids by week 12, or discontinuing the study for any reason will be considered treatment failures. Per-protocol analysis will include participants who completed the 12-week blind treatment course without protocol violations. Missing data were handled using complete-case analysis in the primary analysis. A two-sided p-value of <0.05 will be considered statistically significant. Safety data will be summarized using descriptive statistics. All statistical analyses will be performed using R (4.0.5).

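### Participants randomised but never infused drop out of every planned efficacy analysis, and the plan does not rule out that such exclusions depend on the arm

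*Combined protocol and SAP*

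**What the plan says.** **Analysis sets.** Section 11 (Statistical Analysis) defines two. The first: "A modified intent-to-treat analysis will include all participants who have received at least one FMT treatment". The second is per-protocol, limited to participants who complete the 12-week course without violations. No set of all randomised participants is defined, and no table of participants who never start is planned. Section 11 also counts discontinuation for any reason as treatment failure.

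**Order of events.** Under the screening and group assignment visit in section 5, which spans day -21 to day 0, "Eligible participants were then randomly allocated in a 1:1 ratio to two parallel groups". Infusion follows.

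**Who knows the arm.** The documents disagree.

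- Section 5, Treatment and Follow-Up: "All investigators were aware of group allocation, while endoscopists, pathologists, and outcome assessors remained fully blinded to group assignments to minimize assessment bias".
- Section 7, Blinding Maintenance, first sentence: "participants will be blinded to the identity of the FMT donor, while investigators will be aware of the donor identity".
- Section 7, Blinding Maintenance, next sentence: "The donor's identity will only be accessible to a limited number of staff responsible for preparing the FMT solutions".
- Section 7, on emergencies, gives investigators access to the allocation when urgent care requires it. That provision would be unnecessary if they already had it.

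**Product.** Section 5 describes fresh material from a Han or a Bai donor, so supply is specific to the arm.

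**The concern.** Leaving out people who were never treated is usually defensible when the decision to start cannot be influenced by the allocation. This plan does not establish that condition, for two reasons.

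1. **Staff knowledge.** If staff who can influence whether a first infusion goes ahead know the arm, the choice of who starts may differ between arms.
2. **Supply.** Donors must pass a long list of exclusions, some of them temporary (recent antibiotics, vaccination or travel). The material is used fresh. Availability could therefore differ between Han and Bai donors even if all staff act properly.

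Blinded participants' own decisions should not depend on the arm, so the concern is confined to these two routes. What is at stake is the comparability of the randomised groups. If the participants lost before infusion differ in prognosis between arms, the comparison in the modified ITT set is no longer protected by randomisation. The per-protocol set is narrower still, so no planned analysis would show the problem.

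**Working it through.** **Inputs from the documents.** 50 per arm (section 10). Two-sided 0.05, chi-square or Fisher's exact test (section 11). The plan gives no response rate, effect size, power or expected number of non-starts, so it has no figure of its own to reproduce on this point.

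**Assumptions.** True success rate p = 30% in both arms (range 20% to 40%). k participants in one arm are never infused, with k = 2, 5 or 10.

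**Step 1: worst case.** All k non-starters are in one arm and all would have failed. Successes stay at 50p while the denominator falls to 50 - k, so the spurious gain is 50p/(50 - k) - p = pk/(50 - k). At p = 30%:

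- k = 2: 15/48 = 31.25%, a gain of about 1.3 points
- k = 5: 15/45 = 33.3%, a gain of 3.3 points
- k = 10: 15/40 = 37.5%, a gain of 7.5 points

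The type I error below comes from exact enumeration of two binomials with 50 per arm and no true difference. Would-be failures are removed from one arm, and chi-square is taken without continuity correction.

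| p | k | Spurious gain (points) | Chi-square error | Fisher error |
|---|---|---|---|---|
| 20% | 2 | 0.8 | 0.055 | 0.039 |
| 20% | 5 | 2.2 | 0.062 | 0.043 |
| 20% | 10 | 5.0 | 0.091 | 0.073 |
| 30% | 2 | 1.3 | 0.053 | 0.040 |
| 30% | 5 | 3.3 | 0.064 | 0.052 |
| 30% | 10 | 7.5 | 0.124 | 0.108 |
| 40% | 2 | 1.7 | 0.058 | 0.042 |
| 40% | 5 | 4.4 | 0.074 | 0.061 |
| 40% | 10 | 10.0 | 0.177 | 0.133 |

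With nobody dropped (k = 0), the chi-square error is 0.050 to 0.052 and the Fisher error 0.028 to 0.032 over the same rates.

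**Step 2: non-starting unrelated to prognosis.** The expected rate among those infused is p(50 - k)/(50 - k) = p. Dropping the non-starters then causes no expected bias, whatever k is.

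**Step 3: what the remedy does in each case.** In the worst case, counting non-starters as failures restores 15/50 = 30%. If non-starts in one arm are instead caused by supply and unrelated to prognosis, counting them as failures gives p(50 - k)/50:

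- k = 5: 13.5/50 = 27%
- k = 10: 12/50 = 24%

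That is a spurious loss of 3 or 6 points, similar in size to the gain in step 1. Neither set is right in every scenario.

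**The case against.** A reader might infer that investigators know the arm before the first infusion and that the planned comparison is therefore biased. The documents do not support that.

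- **Timing.** Nothing dates investigator knowledge to before infusion, and the restriction to preparation staff and the emergency provision point the other way. Allocation could also fall on the day of the first infusion, leaving almost no gap.
- **Numbers.** No section describes donor shortage, delays that differ by arm, or discretion to withhold a first infusion. Nothing shows that more than a handful would go untreated.
- **Size.** The larger figures need up to 10 of 50 lost, all in one arm and all would-be failures.
- **Remedy.** Counting supply-driven non-starts as failures can bias the other way, so the choice of primary set is partly a choice of estimand.

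All of this stands, and it makes the point conditional. It does not remove it: the exclusion is explicit, two statements say that investigators are aware, and nothing planned would show whether the condition failed.

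A reader might also see a contradiction between this set and the rule that discontinuation is failure, since leaving just before infusion removes a participant while leaving just after counts as failure. That rule follows the definition of the set and can be read as classifying outcomes within it. It does not clearly bring the uninfused back in, but the two rules do not conflict.

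Finally, complete-case handling with 30 of 50 per arm planned to complete may be a larger loss. It is a separate matter and does not settle this one.

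**Conclusion.** The point holds as a gap in the plan, not as a demonstrated bias. Participants randomised but not infused leave both planned efficacy sets. The documents contradict themselves on whether investigators know the arm and do not say when they learn it. Arm-dependent exclusion is therefore possible, through staff knowledge or through donor supply.

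The size cannot be derived from the documents. At an assumed 30% success rate, one or two non-starters matter little even in the worst case. Five or more selectively lost from one arm begin to matter. If non-starting is unrelated to prognosis, the expected bias is zero. If investigators prove to be blinded, the staff route weakens, but the supply route and the missing all-randomised analysis remain. The change is cheap and should be made; the point does not by itself undermine the trial.

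**What to change.** 1. **Reconcile the blinding text.** Make section 5 (Treatment and Follow-Up) and section 7 (Blinding Maintenance and the emergency provision) agree on who knows the allocation, and state from when.
2. **Add an all-randomised analysis in section 11.** Analyse every randomised participant by allocated donor, with those never infused counted as failures. Preferably make this the primary set, because investigators are stated to be unblinded. Say explicitly that the complete-case rule does not remove these participants.
3. **Report the at-least-one-infusion set beside it.**
4. **Tabulate non-starts by arm**, with number and reason, separating donor or preparation availability from other causes.

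**Cost.** SAP wording, one more analysis and one table. The only extra data item is the reason for not starting. The downside is that success rates fall somewhat, and supply-driven non-starts in one arm would lower that arm's rate (from 30% to 27% for 5, or 24% for 10, as worked above). The two sets must therefore be read together with the table of reasons.

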#### Prohibited Medications:

- Rectal corticosteroids (2 weeks before and throughout the study).
- Antibiotics, antifungals, antivirals, probiotics, or prebiotics (4 weeks before and throughout the study).
- Biologics or calcineurin inhibitors (12 weeks before and throughout the study).

Participants using prohibited medications during the study will remain enrolled, and outcomes will still be evaluated. All prohibited medication usage will be recorded.

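### Any protocol violation, however minor, is scored as treatment failure, and no responder analysis uses the violator's observed week-12 result

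*Combined protocol and SAP*

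**What the plan says.** Section 11 (Statistical Analysis) defines the main set thus: "A modified intent-to-treat analysis will include all participants who have received at least one FMT treatment". The failure rule follows. It covers "Participants requiring additional treatment, violating the study protocol, failing to discontinue corticosteroids by week 12", and its last category and consequence are "discontinuing the study for any reason will be considered treatment failures". No definition, grading or relevance test for a violation is given there or elsewhere. The second set is described as follows: "Per-protocol analysis will include participants who completed the 12-week blind treatment course without protocol violations".

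The Prohibited Medications list (Section 4, Study Population) states: "Participants using prohibited medications during the study will remain enrolled, and outcomes will still be evaluated". Its entries differ in kind. One is "Antibiotics, antifungals, antivirals, probiotics, or prebiotics (4 weeks before and throughout the study", which includes drugs that can be taken for reasons other than UC. The others, "Rectal corticosteroids (2 weeks before and throughout the study" and "Biologics or calcineurin inhibitors (12 weeks before and throughout the study", cover drugs that may be treatment for UC.

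The Treatment and Follow-Up text in Section 5 says that investigators know the group allocation, while endoscopists, pathologists and outcome assessors are blinded. Nobody is named to decide, blind to arm, who has violated the protocol.

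**The concern.** The primary outcome is a yes/no composite of steroid-free clinical remission with endoscopic improvement at week 12, read by blinded assessors. Under the failure rule that reading is replaced by failure whenever a violation is recorded. A participant in steroid-free remission who took an antiviral for influenza, or an over-the-counter probiotic, scores the same as one who needed rescue for active UC. The per-protocol analysis does not recover the result, because it leaves the participant out.

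Two things are at stake. First, the modified ITT responder rate becomes a mixture of remission and compliance. Second, the compliance part rests on an undefined judgement open to people who know the donor group. If violations occur, or are recorded, more often in one arm, the donor comparison is biased in a direction that cannot be predicted.

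The clause can also reach ordinary participants, because the documents disagree on what complies:

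- **Biologics.** Exclusion criterion 12 bars them for 4 weeks before the first FMT, the Prohibited Medications list for 12 weeks. Someone whose last dose was 6 weeks earlier passes the first and breaches the second.
- **Oral steroids.** Permitted Medications has them stopped by week 8, while Section 11 tests for this at week 12. Someone who stops at week 10 passes the steroid clause but has departed from the taper, and may be a failure as a violator.

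**Working it through.** **Tracing a violator's result.** Take a treated participant who has a week-12 assessment and meets the primary definition, but has one recorded violation.

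- Modified ITT: included, scored as failure.
- Per-protocol: excluded.
- Complete-case handling in Section 11: no effect, since the result is not missing.
- Any other responder analysis: none described.

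Section 11 does not say which set is primary, but the observed result is unused under either. Rescue does not need the violation clause, because additional treatment, steroid failure and study discontinuation are listed separately.

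**Inputs for the illustration.** From the documents: 50 per arm (Section 10), 1:1 allocation (Section 5), two-sided 0.05 (Section 11). Section 10 gives no response rates, effect size or power, so the sample size of 100 cannot be reproduced. No violation rate is given either. Assumed: the true response rates p, the violation rates v, and independence of violation and response.

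**Formula.** Scored rate = p × (1 − v).

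| True rates | Violations | Scored rates | Difference (points) |
|---|---|---|---|
| 50% v 30% | 10% v 10% | 0.50×0.90 = 45%; 0.30×0.90 = 27% | 18 |
| 50% v 30% | 20% v 20% | 0.50×0.80 = 40%; 0.30×0.80 = 24% | 16 |
| 50% v 30% | 15% v 5% | 0.50×0.85 = 42.5%; 0.30×0.95 = 28.5% | 14 |
| 50% v 30% | 5% v 15% | 0.50×0.95 = 47.5%; 0.30×0.85 = 25.5% | 22 |
| 40% v 40% | 15% v 5% | 0.40×0.85 = 34%; 0.40×0.95 = 38% | 4, spurious |
| 40% v 40% | 25% v 5% | 0.40×0.75 = 30%; 0.40×0.95 = 38% | 8, spurious |

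**Responders recoded.** 50 × v × (0.50 + 0.30) = 4 of 100 participants at v = 10%, and 8 at v = 20%.

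**Power with equal violation rates, 50 per arm.** With d the difference and p̄ the mean of the two rates, power = Φ{[d − 1.96 √(2p̄(1−p̄)/50)] / √(p₁(1−p₁)/50 + p₂(1−p₂)/50)}.

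- No violations: (0.20 − 0.192)/0.0959 = 0.08, power 53%.
- 10% in each arm: (0.18 − 0.188)/0.0943 = −0.09, power 47%.
- 20% in each arm: (0.16 − 0.183)/0.0919 = −0.25, power 40%.

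For assumed rates of 55% v 30% the corresponding powers are 72%, 64% and 56%.

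**Rejection rate with no true difference.** Exact binomial enumeration of the uncorrected chi-square test at 50 per arm:

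| True rate, both arms | No violations | 10% v 10% | 15% v 5% | 25% v 5% |
|---|---|---|---|---|
| 30% | 5.0% | 5.1% | 6.4% | 10.6% |
| 40% | 5.2% | 5.0% | 7.0% | 13.3% |
| 50% | 5.7% | 5.6% | 8.7% | 18.2% |

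Equal violation rates cost power only. Unequal rates raise the false-positive rate.

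**The case against.** The strongest defence is that this is a composite strategy, conservative and partly deliberate. Rectal corticosteroids, biologics and calcineurin inhibitors may be rescue for UC, and scoring their use as failure is accepted practice. Antibiotics can also be given for UC, as exclusion criterion 10 recognises. Antibiotics, probiotics and prebiotics act on the microbiota, which is what FMT is meant to change, so a responder who took them has not clearly responded to the donor material. Participants and assessors are blinded and both arms receive FMT, so unequal drug use is not an obvious expectation. The trial calls itself a pilot, and moderate violation rates have modest effects. All of this stands as a case for scoring selected violations as failure. It does not justify scoring every undefined violation so, and it does not answer unequal recording by investigators who know the allocation.

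Four stronger readings are tempting, and the documents do not support them:

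- **That violators' outcomes enter no analysis at all.** Section 11 removes no violator from the comparisons of continuous variables, the microbiota outcomes or the safety summaries, and a failure score cannot enter a mean.
- **That Section 11 contradicts the Prohibited Medications section.** One governs scoring, the other retention and evaluation. A result can be collected and still be scored as failure.
- **That the rule always shrinks the donor difference.** It does so at equal rates. With more violations in the poorer arm the difference grows, from 20 to 22 points above.
- **That violations are unrelated to UC.** Some are and some are not, and the rule does not distinguish them.

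**Conclusion.** The point holds for the responder endpoints, including the primary. As written, the rule turns participants whom blinded assessors found to be responders into failures on an undefined judgement, and no planned analysis shows what happens without that step. This is a stated rule that can give a wrong result, and not merely missing detail.

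The size cannot be known from the documents. On the assumptions above, the loss is moderate at equal violation rates: 2 points of difference and about 6 points of power at 10%. The more serious risk is imbalance between arms, which can move the difference either way or lift the rejection rate from about 5% to 7% (15% v 5%) or 13% (25% v 5%) when the true rate is 40% in both. Independence of violation and response is itself an assumption. The change is a cheap improvement worth making before unblinding.

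**What to change.** In Section 11:

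1. Replace the general violation clause with a list, fixed before unblinding, of the violations that count as failure: those that are additional or escalated treatment for UC, whatever the drug class. State in advance how other microbiota-active drugs are scored. Deleting the clause and relying on a short drug list would be too blunt, since it could miss antibiotics given for UC or a raised 5-aminosalicylate dose.
2. Have violations classified by people blind to arm.
3. Score all other violations by the observed week-12 outcome.
4. Add a sensitivity analysis of all treated participants with a week-12 assessment, by observed outcome regardless of violation.
5. Keep the per-protocol analysis as a check.

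Also reconcile the passages that leave violation status ambiguous: the biologic washout in the exclusion criteria and the Prohibited Medications list, and the steroid stop in Permitted Medications (week 8) and Section 11 (week 12). Which clinical rule applies is for the sponsor to settle.

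The cost is SAP wording and a blinded classification step, since the protocol already has these outcomes evaluated. The small downside is that some counted responders will have had a minor or non-UC violation, which the per-protocol analysis checks.

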#### 12. Potential Risks

There is a potential risk of perforation during colonoscopy, but the overall incidence of

complications is less than 1%. The risk of infectious diseases during fecal microbiota transplantation (FMT) is minimal due to rigorous donor screening prior to transplantation. To date, FMT appears to be safe. Over 200 FMT procedures have been conducted at the Academic Medical Center in Amsterdam and more than 3,000 at the Digestive Disease Center in Sydney, Australia, without any reports of serious adverse events. Mild adverse reactions such as bloating, flatulence, borborygmi, vomiting, and abdominal discomfort may occasionally occur. Only qualified researchers have access to de-identified data in the database. Furthermore, they agree not to use this information to attempt to identify the data providers, ensuring participant confidentiality. However, given the availability of current public-domain technologies and expected advancements in the coming years, identifying specific individuals from genetic or other information may become feasible and increasingly straightforward. Participants and their family members may face potential risks (e.g., those related to insurance, employment, cybersecurity breaches, and law enforcement) due to shared genetic characteristics.

### 13. Pregnancy

All women of childbearing potential, except postmenopausal or sterilized women, are required to undergo pregnancy testing. Women of childbearing potential must use contraception throughout the study. If a female participant becomes pregnant during the study, she must immediately notify the research team. In such cases, the participant will be withdrawn from the study. If feasible, an early termination visit will be scheduled after pregnancy confirmation.

### 14. Non-return of Research Results

The results of microbiome analyses will not be returned to participants. In other words, this data will not be used to influence the clinical care received by participants or their genetically related family members. The potential benefit of this study lies in improving care and management in the future.

### 15. Costs, Expenses, and Compensation

To assist participants with costs related to research participation, including travel and other expenses, fecal microbiota transplantation (FMT) will be provided free of charge during each required study visit. The total cost of the three FMT procedures is estimated to be 18,000 RMB.

